6.5 Pharmacokinetic Evaluations

Not applicable.

6.6 Safety Evaluations

Safety analyses will be conducted using the Safety Analysis Set.

6.6.1 Adverse Events

Adverse events (AEs) will be coded using the Medical Dictionary for Regulatory Activities (MedDRA), see Section 5.1, and displayed in tables and listings using System/Organ/Class (SOC) and Preferred Term (PT).

Analyses of adverse events will be performed for those events that are considered treatment emergent, where treatment emergent is defined as any adverse event with onset after the administration of study medication through the end of the study (see Section 5.2) or any event that was present at baseline but worsened in intensity or was subsequently considered drug-related by the investigator through the end of the study.

Adverse events are summarized by subject, therefore, in any tabulation, a subject contributes only once to the count for a given adverse event (SOC or preferred term).

The number and percentage of subjects with any treatment-emergent adverse event (TEAE), any treatment-emergent adverse event by severity, with any treatment-emergent adverse event by relationship to study drug, with any treatment-emergent adverse event leading to withdrawal from study drug, and with any treatment-emergent serious adverse event (SAE) will be summarized by treatment group and overall. In these tabulations, each subject will contribute only once (i.e., the most related occurrence or the most intense occurrence), regardless of the number of episodes. The number of events and the average number of events will also be provided in tabulations of TEAEs and serious TEAEs.

Adverse events with definite, probable, and possible relationship are considered related to study drug. Adverse events with unrelated and unlikely relationship are considered unrelated to study drug.

Histograms showing the frequency of the number of treatment-emergent AEs and SAEs in each treatment group will be included.

Exposure-adjusted event rates by treatment group and overall will be provided for participants with TEAEs, and with serious TEAEs. Each summary will present by decreasing incidence of PT per 100 subject years of exposure, calculated as (number of subjects with event/total patient-years). Years of exposure is either a) time from first treatment until start date of TEAE type or b) duration of exposure for subjects without a TEAE type. Poisson regression modeling will be used to derive rate ratios and 95% CIs for each SOC. Rate ratios will be compared using a two-sided 0.05 level test for Poisson count data.

The number and percentage of subjects with TEAE with hospitalization required will be summarized by treatment group and overall, including the number of events, the average number of events and the exposure-adjusted event rates. Poisson regression modeling will be used to derive rate ratios and 95% CIs to compare hospitalization rates between treatment groups.

All adverse events occurring on study will be listed in subject data listings.

By-subject listings also will be provided for the following: subject deaths; serious adverse events; adverse events leading to withdrawal and adverse events with hospitalization required.

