8.2.3.2 RELATIONSHIP TO STUDY INTERVENTION

The study uses the following AE attribution scale:

Definite: AE is clearly related to study drug or a study procedure

Probable: AE is likely related to study drug or a study procedure

Possible: AE is possibly related to study drug or a study procedure

Unlikely: AE is doubtfully related to study drug or a study procedure

Unrelated: AE is clearly not related to study drug or a study procedure

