9.4.4 SAFETY ANALYSES

All reported (S)AEs will be coded using MedDRA and grouped by body system. (S)AEs will be tabulated by treatment group using standard coding terms. Incidence of AEs by treatment arm will be tabulated by seriousness, severity, and relationship to study drug. If an AE is reported more than once for a given subject, the greatest severity and the worst-case relationship will be presented in tables. The number of SAEs and AEs will be summarized for each treatment group as follows: (i) The proportion of subjects with at least one (S)AE, (ii) The average number of (S)AEs per subject, and (iii) The rate of (S)AEs per

subject week of follow-up. Histograms showing the frequency of the number of (S)AEs in each treatment group will be included. Rates of (S)AEs by System Organ Class (SOC) will be presented by treatment group. Poisson regression modeling will be used to derive rate ratios and 95% CIs for each SOC. Rate ratios will be compared using a two-sided 0.05 level test for Poisson count data.

Safety lab data at each study visit and changes from baseline will be summarized by treatment group. In addition, clinical laboratory summaries will be presented by treatment group including: (i) incidence of significant abnormalities by visit; (ii) tables summarizing the frequencies of subjects below, within, and above the normal reference ranges at baseline and end of study; and (iii) tables displaying baseline to end of study shifts in each laboratory value (shifts between below, within or above normal range).

Although drug discontinuation is anticipated to be infrequent, the proportion of subjects permanently discontinuing study drug will be tabulated by treatment group. Drug discontinuation events will be categorized as: (1) Permanently discontinued study drug and (2) Permanently discontinued study drug and withdrew from study. The reason for permanent drug discontinuation will be summarized. The number of hospitalization events and proportion of subjects hospitalized from baseline to study termination will be summarized and compared by treatment group. Poisson regression modeling will be used to derive rate ratios and 95% CIs to compare hospitalization rates between treatment groups.

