6.2.6 Missing, Unused, and Spurious Data

The handling of intercurrent events (ICEs) and sensitivity analyses are described in Section 6.4. No other imputation of missing efficacy endpoints will be used.

In all listings, missing or incomplete dates in safety data will be left as they have been recorded. However, for calculation and sorting based on dates and for consideration in summary tables, the following method will be used:

For partial or missing adverse event (AE) start dates the following imputation will be applied:

1. If year is not missing and is after the year of first dose:
 - a. If month is missing, then month will be imputed as January.
 - b. If day is missing, then day will be imputed as the first of the month.

2. If year is not missing and is the same as the year of the first dose:
 - a. If month is missing, then impute the month as the month of the first dose date.
 - b. If day is missing, and the month is the same as the month of the first dose date, then impute day as the day of the first dose date.
 - c. If day is missing but month is after the month of first dose date, then impute day as the first day of the month.
3. If year is missing then impute the year as the year of the first dose date:
 - a. If month is missing, then impute the month as the month of the first dose date.
 - b. If day is missing, then impute the day as the day of the first dose date.
4. If the start date is completely missing, but the AE is either ongoing or the stop date is after the first dose date then impute the start date as the first dose date.
5. For any cases involving the rules above, if the AE end date is before the AE start date, then do not impute the AE start date and assume that the AE is treatment emergent for the purpose of the analysis. Further, if the AE stop date occurs prior to the first dose date, do not impute the AE start date, and assume that the AE is not treatment emergent.

No imputations will be applied to AE stop dates.

A missing/incomplete date of medical comorbidities or disease diagnosis will be assumed to have occurred before any study treatment.

Missing AE relationship data will be assigned the 'related' category for treatment emergent AE.

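### The protocol's causality scale covers study drug and study procedures together, but the SAP reads its upper three levels as drug-related, so a Week 24 procedure complication can enter the drug-related TEAE table

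*SAP*

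**What the plan says.** **Scale.** Protocol 8.2.3.2 gives one five-level scale. Its top level reads "Definite: AE is clearly related to study drug or a study procedure". The lowest level that the SAP later counts as related reads "Possible: AE is possibly related to study drug or a study procedure". The other three levels use the same drug-or-procedure pairing. Neither document describes a separate rating for procedures.

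**Mapping.** SAP 6.6.1 says: "Adverse events with definite, probable, and possible relationship are considered related to study drug". Each subject is counted once in the relationship table, at the strongest relationship recorded. For gaps, SAP 6.2.6 says: "Missing AE relationship data will be assigned the 'related' category for treatment emergent AE".

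**Planned tables.** Protocol 9.4.4 says: "Incidence of AEs by treatment arm will be tabulated by seriousness, severity, and relationship to study drug". Its scope is wide: "All reported (S)AEs will be coded using MedDRA and grouped by body system". Protocol 8.2.4 records events from consent onward. SAP 6.6.1 is narrower: "Analyses of adverse events will be performed for those events that are considered treatment emergent". By its definition, an event qualifies if it begins once dosing has started and no later than the end of study. The SAP also admits an event present at baseline that later worsens or that the investigator later considers drug-related. SAP Section 7, which lists changes from the protocol, does not mention the narrowing.

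**The concern.** The rating that is collected answers a different question from the one the table reports. An investigator who follows Protocol 8.2.3.2 and is sure that a neck hematoma came from the research catheterization should choose the top level. The SAP then reports that event as related to famotidine or placebo.

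At stake is the meaning of the drug-related column in the safety tables of a small Phase II trial. In addition, the protocol (2.3.1) acknowledges a small risk of serious complications from the optional procedures, yet the SAP text describes no table that would show those complications as such.

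**Working it through.** The documents state no figure on this point, so there is none to reproduce. The check follows the definitions and then sizes the exposure.

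**1. A Week 24 procedure complication.** Protocol 8.1 requires the Week 24 catheterization and exercise test to be done on study drug. A complication therefore has its onset after dosing and is treatment emergent if it begins by the end of study, which SAP 5.2 defines as the last recorded visit.
- Graded definite, probable or possible: related to study drug under SAP 6.6.1.
- Relationship missing: related under SAP 6.2.6.
- Graded unlikely or unrelated: not affected.

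If it is the subject's strongest rating, it also sets that subject's entry in the relationship table.

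**2. A baseline procedure complication.** Baseline procedures precede Day 0. The event is collected (Protocol 8.2.4) and falls within the protocol's tabulation of all reported events (9.4.4). Under SAP 6.6.1 it is not treatment emergent, so it appears in the by-subject listings but in no summary table that the SAP text describes for the final analysis. The exception is an event that worsens or is later judged drug-related. That judgement is one the combined scale cannot record separately.

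**3. Number of procedures.** The schedules of activities plan n = 20 catheterizations and n = 10 exercise tests, each at baseline and at Week 24.
- Per time point: 20 + 10 = 30 at most.
- Participants involved: 20 (full overlap) to 30 (none), that is 20/80 = 25% to 30/80 = 37.5%.

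**4. Expected number of misattributed events.** The documents give no complication rate; Protocol 8.2.3.3 calls these events uncommon. With an assumed probability p per procedure, independent procedures, and every complication treatment emergent and graded possible or higher:

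expected events = 30p; chance of at least one = 1 − (1 − p)^30

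| Assumed p | Expected at Week 24 | Chance of at least one |
|---|---|---|
| 1% | 0.3 | 0.26 |
| 5% | 1.5 | 0.79 |
| 10% | 3 | 0.96 |
| 20% | 6 | >0.99 |

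**5. Balance between arms.** Randomization is stratified by functional class only. With 40 per arm and 20 catheterization participants taken as a random draw from the 80, the number in one arm is hypergeometric: P(k) = C(40,k)·C(40,20−k)/C(80,20). Summed over both tails, a split of 12–8 or worse has probability 0.44, and 13–7 or worse 0.20. Protocol 8.1 places randomization of sub-study participants at their last baseline assessment, so this is chance imbalance at entry and not a systematic one.

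**The case against.** The strongest reply is that the source may be sound even if the text is not. The CRF is not among the documents, and the list of statistical outputs (SAP Section 10) was not available for this review. A separate procedure field or table may exist. Both documents name the table axis as relationship to study drug, so investigators may already be recording that. This stands, and the fix allows for it; the written definitions still disagree.

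Four stronger inferences are tempting, and the documents do not support them.

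- **Every post-dose procedure complication becomes a drug reaction.** Only those graded possible or higher, or left ungraded, do. A few may also start after the last recorded visit, since the procedures may fall up to 7 days from the Week 24 visit. The 20 and 10 are planned numbers in optional sub-studies.
- **False events could dominate the drug-related table.** No rate in the documents supports this, and the upper end of the assumed range sits poorly with the description of these events as uncommon. Headache is not the only known famotidine effect: Protocol 2.3.1 adds gastrointestinal upset and rare allergic reactions.
- **Procedure risk could not be estimated, or pre-dose events are lost.** All adverse events stay in listings (SAP 6.6.1), and the DSMB reports summarize all SAEs and AEs with no stated treatment-emergent limit (Protocol 9.4.6, SAP 2.5). Complications of about 60 procedures at one center can be counted from listings. Leaving pre-dose events out of drug tables is conventional; the fault is that the change is undeclared and no other final table picks these events up.
- **The safety comparison between arms is biased.** The Poisson comparisons, by SOC and for hospitalization, do not select events by causality rating. The relationship table is descriptive.

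**Conclusion.** The point holds as a conflict of definitions: a correctly graded procedure complication is given the wrong label by a stated SAP rule. It touches one descriptive table and, within it, possibly the single entry of a subject with such an event. The primary 6MWD analysis is untouched.

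The number of mislabelled events is unknown. The range of 0.3 to 6 rests on an assumed 1% to 20% per procedure, on all 30 planned Week 24 procedures taking place, on investigators using the scale as the protocol defines it, and on the CRF holding only the combined rating. If the CRF already separates the two, what remains is a wording correction.

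The undeclared move from all reported events to treatment-emergent events is a secondary documentation gap. Its practical effect is that baseline-procedure complications are normally listed but not summarized. The correction is inexpensive and should be made before unblinding.

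**What to change.** 1. Record two relationships for each adverse event, one to study drug and one to a study procedure, naming the procedure. If the CRF already does this, cite that field in the SAP.
2. In SAP 6.6.1, define related to study drug from the drug rating only. Make the missing-data rule in SAP 6.2.6 refer to the drug rating only.
3. Before unblinding, have the blinded investigator re-attribute events already graded possible or higher. Include events with no recorded relationship, because SAP 6.2.6 would otherwise turn them into related ones.
4. Add one descriptive table of procedure-related AEs and SAEs from consent onward, by procedure and by timing (baseline or Week 24).
5. List the restriction to treatment-emergent events in SAP Section 7.

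Cost: a SAP edit, one table and a small blinded review, with a CRF field if none exists. Amending the scale in Protocol 8.2.3.2 would also need NHLBI and DSMB review (Protocol 10.1.6) and IRB approval (Protocol, Statement of Compliance).

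### Poisson models for adverse events and hospitalizations make no allowance for overdispersion where all events, including repeat events, are counted

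*SAP*

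**What the plan says.** **Protocol 9.4.4** summarizes AEs and SAEs as the proportion of participants affected, the mean number per participant and the rate per subject-week. It then presents rates by SOC, fits Poisson models to them, and adds: "Rate ratios will be compared using a two-sided 0.05 level test for Poisson count data". For hospitalization it compares the number of events and the proportion of participants hospitalized, and again derives Poisson rate ratios with 95% CIs.

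**SAP 6.6.1, AEs by SOC.** The model sentence is the same: "Poisson regression modeling will be used to derive rate ratios and 95% CIs for each SOC". It directly follows an exposure-adjusted rate "calculated as (number of subjects with event/total patient-years"), in which time for a participant with the event is "time from first treatment until start date of TEAE type". The section also counts each participant once per SOC or preferred term in tabulations. Against that, "The number of events and the average number of events will also be provided in tabulations of TEAEs and serious TEAEs".

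**SAP 6.6.1, hospitalization.** The summary gives participants affected, "including the number of events, the average number of events and the exposure-adjusted event rates". Then: "Poisson regression modeling will be used to derive rate ratios and 95% CIs to compare hospitalization rates between treatment groups". It does not say whether first or all hospitalizations enter the model.

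**Variance.** Neither document names a variance estimator for any of these models. Robust standard errors are named only for the complete-case 6MWD model (Protocol 9.4.2, SAP 6.4.1.1). SAP 6.2.4 makes no multiplicity adjustment, and SAP section 7 lists no change from event rates to first-event rates.

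**The concern.** A Poisson model sets the variance of the count equal to its mean. When one person can contribute several events and people differ in their underlying rate, the variance of the count exceeds the mean. Default standard errors are then too small. With no remedy specified, a programmer following Protocol 9.4.4 literally would probably fit all events with default errors.

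What is at stake is the reading of the safety results: a spurious AE difference in some SOC, or a hospitalization rate ratio reported with more precision than the data support.

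**Working it through.** **Inputs from the documents.** Two-sided level 0.05 (Protocol 9.4.4, SAP 6.6.1). 80 participants randomized 1:1, so 40 per arm (SAP 2.2). 24 weeks of treatment (SAP 2.1).

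**Inputs assumed.** The documents give no AE rate, hospitalization rate or dispersion. Let μ be the mean number of events per participant over 24 weeks. Let k be the variance of a gamma-distributed personal rate multiplier with mean 1. Then the variance of the count is μ + kμ², and the ratio of variance to mean is φ = 1 + kμ.

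**Step 1: large-sample formula.** The default Poisson standard error is too small by a factor 1/√φ, so

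actual level = 2[1 − Φ(1.96/√φ)], and actual coverage of a 95% CI = 1 − actual level.

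| φ | Actual level | CI width relative to correct | Coverage |
|---|---|---|---|
| 1 | 0.050 | 1.00 | 95.0% |
| 1.25 | 0.080 | 0.89 | 92.0% |
| 1.5 | 0.110 | 0.82 | 89.1% |
| 2 | 0.166 | 0.71 | 83.4% |
| 3 | 0.258 | 0.58 | 74.2% |

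The first row reproduces the plan's nominal 0.05. It holds only when the variance equals the mean.

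**Step 2: simulation at the trial's size.** 40 per arm, 24 weeks, no treatment effect, 50,000 trials per setting. Three Wald tests were compared: all events with default errors, all events with robust (sandwich) errors, and first events with exposure cut at the event, as the SAP rate is defined.

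| μ | k | φ | All events, default | All events, robust | First event, default |
|---|---|---|---|---|---|
| 0.25 | 0 | 1.00 | 0.043 | 0.043 | 0.040 |
| 0.25 | 1 | 1.25 | 0.068 | 0.051 | 0.039 |
| 0.25 | 2 | 1.50 | 0.093 | 0.054 | 0.038 |
| 0.5 | 1 | 1.50 | 0.102 | 0.057 | 0.049 |
| 0.5 | 2 | 2.00 | 0.153 | 0.062 | 0.050 |
| 1 | 0 | 1.00 | 0.046 | 0.050 | 0.050 |
| 1 | 1 | 2.00 | 0.162 | 0.060 | 0.059 |
| 1 | 2 | 3.00 | 0.249 | 0.063 | 0.059 |

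**Step 3: reading the results.**

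- With all events and default errors, the level rises with both rate and heterogeneity. At low rates the formula overstates the excess: at μ = 0.25, k = 2 it gives 0.110, against 0.093 simulated.
- With first events, the level stays at 0.038 to 0.059 for μ from 0.25 to 1 and k up to 2 (likelihood-ratio test 0.051 to 0.064). It reaches about 0.09 only at μ = 3 with heterogeneity. The cause there is a non-constant hazard, not recurrence.
- With robust errors on all events, the level lies between 0.043 and 0.066 over every setting tried. The maximum is at μ = 3, k = 2, where default errors give 0.454.

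**The case against.** The strongest case on the other side has four parts.

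1. **The SAP's SOC model may not use recurrent events.** Its sentence comes straight after a rate based on participants, with time stopped at the first event. On that reading nothing recurs and the level is close to nominal. This stands. A reader might infer that every SOC test in the SAP rejects too often, and the documents do not support that. They also do not settle the matter: the SAP does not tie the model to that rate, it refers to Poisson count data, and section 7 does not record a departure from the protocol. The hospitalization paragraph could inherit the same first-event rate through the shared term, although its lead-in lists event counts.

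2. **Default errors are nowhere stated.** This stands too. A reader might infer that the plan chose model-based errors, but it is silent. Default errors are the likely result of that silence, because robust errors are named where they are wanted.

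3. **The larger figures need a high rate.** A mean of 1 event per person is more plausible for all AEs together than for one SOC, and hospitalizations may be rarer still. At a mean of 0.25 the simulated level is 0.054 to 0.093 for k from 0.5 to 2. The planned histograms of events per participant are descriptive and do not show that events cluster.

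4. **No efficacy conclusion rests on these models.** A reader might infer a risk of a false claim that famotidine reduces hospitalization. Hospitalization is not among the secondary endpoints in SAP 6.4.2, and no such claim is planned. The effect is confined to the safety results.

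**Conclusion.** The point holds conditionally. Protocol 9.4.4, and SAP 6.6.1 for hospitalization on its event-count wording, apply Poisson regression to events that can recur within a person and make no allowance for overdispersion. Three conditions must all be met for harm: all events are modeled, default errors are used, and participants differ in event rate. The simulated level is then about 0.07 to 0.09 at a mean of 0.25 events per person and 0.16 to 0.25 at a mean of 1, for k from 1 to 2. The hospitalization analysis names a CI rather than a separate test, so there the same figures read as non-coverage of the 95% interval.

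The rates and k are assumptions. The SAP's SOC models are not affected by recurrence if they use the first-event rate. In that case the remaining fault is an unlisted change from the protocol.

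**What to change.** In SAP 6.6.1, state for each Poisson model whether it counts first or all events, and define the matching offset. For all events this is log total time at risk. For first events it is log time to the first event or to the end of exposure. An all-event count should not be paired with time cut at the first event.

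Fit the hospitalization model, and any SOC model that counts all events, as Poisson regression with one record per participant, that offset and robust (sandwich) standard errors. List any departure from Protocol 9.4.4 in SAP section 7.

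This is a cheap improvement: one model option, a few lines of definition and one entry in section 7. The cost is slightly wider intervals where counts are overdispersed, which is the intended correction. Robust errors are not perfect: their simulated level reached 0.066 under the heaviest dispersion tried. They can also be unstable with very few events. The smallest rate simulated corresponds to 40 × 0.25 = 10 expected events per arm, so sparser SOCs were not tested. For those, an exact or purely descriptive comparison can be shown instead.
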